8.8.2 Return and/or destruction of treatments

Partially-used and used study treatment will be destroyed at the study site according to the standard practices of the site after an accurate accountability has been performed and signed by the Investigator (or the Pharmacist). A detailed treatment log form of the destroyed study treatment will be established with the Investigator (or the Pharmacist) and countersigned by the Investigator and the Monitoring Team.

The Investigator must not destroy the unused IMP unless Sanofi provides written authorization.

8.9 CONCOMITANT TREATMENT

A concomitant medication is any treatment received by the patient concomitantly to any study treatment(s).

All treatments being taken by the patient 21 days prior to the first study treatment, at any time during the study in addition to the IMP are regarded as concomitant treatments and the type, dose and route of administration must be documented on the appropriate pages of the e-CRF.

Concomitant medications should be kept to a minimum during the study. However, if these are considered necessary for the patient's welfare and are unlikely to interfere with the IMP, they may be given at the discretion of the investigator and recorded in the e-CRF.

- Supportive treatment as medically indicated for the patient's well-being may be prescribed at the Investigator's discretion. Every medication or treatment taken by the patient during the trial and the reason for its administration must be recorded on the e-CRF.

8.9.1 Prophylaxis for opportunistic infections

A recent study suggests that infections are the leading therapy-related causes of death in MM patients. Based on the NCCN guideline Version 1.2018, MM patients are at an intermediate risk of infection, prophylaxis for opportunistic infections is appropriate in this study. Broad-spectrum antimicrobial agents should be used in high-risk patients, per investigator's discretion.

8.9.2 Prohibited concomitant treatments:

- Concurrent treatment with any other anti-myeloma therapy not specified in the protocol, including immunotherapy, hormonal therapy, targeted therapy or biological therapies, or other investigational drug, or curative radiotherapy. However, palliative radiotherapy may be given to control pain. The irradiated area should be as small as possible and should never involve more than 20% of the bone marrow in any given 3-week period. In all such cases, the possibility of tumor progression should be ruled out by physical, biochemical and radiological assessments of the tumor. The irradiated area cannot be used as a parameter for response assessment.
- Concomitant systemic corticosteroids are prohibited, except used in the premedication as defined in the study protocol Inhaled glucocorticosteroids whenever indicated is allowed.

- Live vaccines should be avoided. However, giving the increased risk of infection, routine vaccinations are recommended for the patients and their contacts. Prophylactic vaccination is recommended for influenza A and B virus, pneumococci and haemophilus influenza.
- Prophylactic use of hematopoietic growth factors (eg, G-CSF, GM-CSF, erythropoietin) during the DLT observation period. Curative treatment is allowed.

8.9.3 Contraceptive measures and pregnancy counseling

Females of child bearing potential or male subjects with female partners of childbearing potential shall be required to use effective contraceptive methods (double barrier method, intrauterine device, oral contraception or abstinence) prior to first study treatment, while on therapy and for 5 months following the last dose of Isatuximab and 6 months following the last dose of cemiplimab.

A woman is considered of childbearing potential (WOCBP), ie, fertile, following menarche and until becoming post- menopausal unless permanently sterile.

The following highly effective methods of contraception are accepted:

- Sexual abstinence,
- Diaphragm and spermicide PLUS male condom, or,
- Intrauterine device PLUS male condom, or,
- Medical method (such as hormonal contraceptive) PLUS male condom.

The choice of effective method is left to Investigator judgment, in accordance to local regulation. Sterilized or infertile subjects are exempt from the requirement to use of contraception. In order to be considered sterilized or infertile, subjects must have undergone surgical sterilization (vasectomy/bilateral tubectomy, hysterectomy, bilateral ovariectomy) or be a postmenopausal woman defined as 12 months or more with no menses prior to enrollment and 50 years of age.

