Appendix J Contraceptive guidance and collection of pregnancy information

No reproductive toxicology studies have been conducted with isatuximab, so the most conservative contraceptive recommendation has to be followed.

DEFINITIONS

Nonreproductive potential

1. Premenopausal female with 1 of the following:
 - Documented hysterectomy.
 - Documented bilateral salpingectomy.
 - Documented bilateral oophorectomy.
2. Postmenopausal:
 - A postmenopausal state is defined as no menses for 12 months without an alternative medical cause. A high follicle stimulating hormone (FSH) level in the postmenopausal range may be used to confirm a postmenopausal state in women not using hormonal contraception or hormonal replacement therapy (HRT). However, in the absence of 12 months of amenorrhea, a single FSH measurement is insufficient.
 - Females on HRT and whose menopausal status is in doubt will be required to use 1 of the highly effective contraception methods if they wish to continue their HRT during the study. Otherwise, they must discontinue HRT to allow confirmation of postmenopausal status before study enrolment.

Reproductive potential

A woman is considered of reproductive potential (WOCBP), ie, fertile, following menarche and until becoming postmenopausal unless permanently sterile. Permanent sterilization methods include hysterectomy, bilateral salpingectomy and bilateral oophorectomy.

CONTRACEPTIVE GUIDANCE

Male subjects

- Male subjects with heterosexual partners of reproductive potential (WOCBP) are eligible to participate if they agree to use the following during the protocol defined timeline:
 - Refrain from donating sperm

and

 - At least 1 of the following conditions applies:
 - Are and agree to remain abstinent from penile-vaginal intercourse on a long term and persistent basis, when this is their preferred and usual lifestyle

or

- Agree to use a male condom plus an additional contraceptive method with a failure rate of <1% per year (see table for female subjects).
- Men with a pregnant or breastfeeding partner must agree to remain abstinent from penile-vaginal intercourse or use a male condom for the time defined in the protocol.

Female subjects:

Highly Effective Contraceptive Methods That Are User Dependent Failure rate of <1% per year when used consistently and correctly^a

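### Protocol 8.9.3 accepts the double barrier method as highly effective, while Appendix J excludes it by implication for men and leaves it out of its table for women

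*Protocol*

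**What the plan says.** **Section 8.9.3** covers women of childbearing potential and men with partners of childbearing potential. Contraception is required before the first dose, during treatment, and for 5 months after the last isatuximab and 6 months after the last cemiplimab dose. The opening paragraph gives the effective methods as "double barrier method, intrauterine device, oral contraception or abstinence". A list of accepted methods follows, described as highly effective: abstinence; "Diaphragm and spermicide PLUS male condom"; an intrauterine device with a condom; and a medical (for example hormonal) method with a condom. The section then says: "The choice of effective method is left to Investigator judgment, in accordance to local regulation". It defines postmenopausal status as "12 months or more with no menses prior to enrollment and 50 years of age". It does not mention Appendix J.

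**Appendix J** opens with the statement "No reproductive toxicology studies have been conducted with isatuximab", and continues "so the most conservative contraceptive recommendation has to be followed". Men with partners of reproductive potential must either be abstinent or "Agree to use a male condom plus an additional contraceptive method with a failure rate of <1% per year (see table for female subjects"). The table for women has two blocks, the first headed "Highly Effective Contraceptive Methods That Are User Dependent" and the second for user-independent methods.

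**Links between the two.** Exclusion criterion E 18 sends the reader to Appendix J, both in the protocol summary and in Section 7.3. Section 17 makes the appendices part of the protocol.

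**The concern.** Two parts of one protocol use the label highly effective for different sets of methods. Section 8.9.3 is the section on contraceptive measures during treatment. Someone at a site who consults only that section will find the double barrier method named twice and accepted, with the choice left to the investigator.

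What is at stake is avoidable fetal exposure to a drug that, by Appendix J's own account, has had no reproductive toxicology studies. The other safeguards act after the event. Pregnancy tests (Section 1.1, footnote i) detect a pregnancy but do not prevent one, and they are scheduled for female patients only. For a male patient's partner the protocol schedules no test. It relies on reporting a partner's pregnancy as an adverse event of special interest (Section 10.5).

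**Working it through.** No arithmetic is involved beyond a count, so the check sets the texts side by side.

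1. **Is the method accepted in 8.9.3?** Yes. It appears as the double barrier method in the opening paragraph and as diaphragm, spermicide and condom in the list of accepted methods. Both apply to women and to men with partners of childbearing potential.

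2. **What does the Appendix J table contain?**
   - User dependent, 2 entries: combined hormonal; progestogen-only hormonal.
   - User independent, 6 entries: progestogen implant; IUD; IUS; bilateral tubal occlusion; vasectomized partner; sexual abstinence.
   - Total 2 + 6 = 8 entries, none of them a barrier method.

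3. **Men.** A man who is not abstinent needs a condom plus a second method below 1% failure per year, with the table given as the reference for that method. Diaphragm and spermicide is not in the table. Condom plus diaphragm and spermicide therefore satisfies 8.9.3 but not Appendix J. The step relies on reading the table as the complete set of qualifying methods. Appendix J does not name the diaphragm, and neither document gives a failure rate for it.

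4. **Women.** The table follows directly under the heading for female subjects. No sentence there says that unlisted methods are refused. This is an omission, not a stated exclusion.

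5. **Which text governs?** The conservative-recommendation instruction, the pointer in E 18 and Section 17 all favour Appendix J. Against that, E 18 is an entry criterion and recruitment has finished. Section 8.9.3 neither repeats the instruction nor refers to the appendix.

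6. **Are the two texts both current?** Yes. Appendix K explains how the mismatch probably arose. Amendment 03 added Appendix J and the reference in E 18, and its entry does not list 8.9.3. Amendment 04 changed only the duration in 8.9.3. The mismatch itself lies wholly in text now in force.

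7. **Does it still apply to anyone?** It can. The Amendment 05 rationale says patients who benefit stay on treatment, and Section 12.4.5 provides for treatment beyond the final cut-off. Amendment 06 was written so that dosing can continue with a replacement cemiplimab vial.

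**The case against.** The strongest reply is that the protocol already resolves the matter. Appendix J tells sites to follow the most conservative recommendation, E 18 directs them to it, and Section 17 gives it the force of the protocol. Appendix J's rule for men is also worded as a condition of eligibility, so a site applying E 18 after Amendment 03 should have obtained the man's agreement at entry. On this view a site accepts the method only by overlooking E 18 and Appendix J.

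Much of that stands, and it is why Appendix J should be taken as the governing text on this method. It does not make 8.9.3 correct. That section still says the method is accepted, gives no pointer, and leaves the choice to the investigator.

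A reader might infer a direct contradiction for both sexes. The documents do not support that: the conflict for men is by implication, and for women there is only an omission. A reader might also treat the number of options in each list as a measure of the problem. It is not one, because 8.9.3 lists combinations and Appendix J lists single methods.

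A further objection is sound. A bare cross-reference to Appendix J would expose other differences without settling them. Section 8.9.3 adds a condom to the IUD and to hormonal methods, and the women's table does not. Section 8.9.3 puts an age condition on postmenopausal status, and Appendix J does not. Section 8.9.3 exempts subjects after vasectomy or tubectomy, while Appendix J treats a vasectomized partner and tubal occlusion as methods. The fix has to say which requirement applies.

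**Conclusion.** The point holds as a limited inconsistency in an operative safety instruction. Section 8.9.3 accepts a method that Appendix J excludes by implication for non-abstinent men and does not list for women.

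Those affected are patients of reproductive potential, or men with such partners, who use the double barrier method and are either on treatment or within 5 months of the last isatuximab or 6 months of the last cemiplimab dose. The documents do not give their number. It is probably very small: enrolment is closed, since the Amendment 05 rationale reports an analysis at 1 year after the last patient in, and Section 4.1.3 puts more than 80% of myeloma patients at age 60 or older.

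The conclusion assumes that the table is the full set of methods meeting Appendix J's failure-rate condition, and that some sites consult 8.9.3 on its own. The documents do not show how many do, or that any patient has used the method. Nothing here supports an inference that trial results are at risk: no efficacy or safety analysis changes.

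**What to change.** In Section 8.9.3:

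- delete the double barrier method from the opening paragraph and the diaphragm and spermicide option from the list;
- add a reference to Appendix J for acceptable methods;
- add one sentence saying that where 8.9.3 and Appendix J differ, the stricter requirement applies. The condom added to an IUD or medical method and the age-50 condition then stay in force.

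E 18 needs no change, as it already points to Appendix J and enrolment is closed.

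Make the change with the next amendment and notify sites that have patients on treatment or within the 5-month or 6-month period. The cost is a short text change with written IRB/IEC approval before implementation (Section 17), a consent-form update only if the form names the method, and a note to at most about 37 sites (the expected number in the protocol summary).

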9 ASSESSMENT OF INVESTIGATIONAL MEDICINAL PRODUCT

9.1 SAFETY

The first co-primary objective of this study is to determine the safety and tolerability of the combination of isatuximab and cemiplimab in patients with RRMM.

The safety profile will be assessed from the findings of physical examination (preferably by the same physician in each center), laboratory tests and reports of AEs, etc, and will be based on incidence, severity (as graded by the NCI-CTCAE v. 4.03), and cumulative nature of TEAEs (defined as AEs that develop or worsen in grade or become serious during the TEAE period).

9.1.1 Dose-limiting toxicities (Phase 1 only)

Potential DLTs are defined as the occurrence of any of the following adverse reactions at first cycle:

Hematological DLT is defined as any of the followings unless due to disease progression or an obviously unrelated cause:

- Grade 4 neutropenia lasting more than 7 consecutive days.
- Grade 3 to 4 neutropenia complicated by fever (temperature $\geq 38.5^{\circ}\text{C}$ on more than one occasion) or microbiologically or radiographically documented infection.
- Grade 3 to 4 thrombocytopenia associated with clinically significant bleeding that requiring clinical intervention.

Note: Platelet transfusions in the absence of bleeding will not be considered a DLT because thrombocytopenia is an anticipated complication of MM, particularly in a heavily pretreated patient population, and patients can enter the study with pre-existing thrombocytopenia.

Non-hematologic DLT is defined as any of the followings unless due to disease progression or an obviously unrelated cause:

- Grade 4 non-hematologic AE.
- Grade ≥ 2 uveitis.
- Grade 3 non-hematological AE lasting >3 days despite optimal supportive care. **except:**
 - Grade 3 fatigue,
 - Allergic reaction/hypersensitivity attributed to isatuximab or cemiplimab,
 - Laboratory abnormality that worsens to Grade 3 or 4 but is not clinically significant per investigator and study committee.
- Delay in initiation of the 2nd cycle >14 days due to treatment related laboratory abnormalities/ AE.

In addition, any other AE that the investigator / Study Committee deem to be dose limiting, regardless of its grade, may also be considered as DLT.

At the end of Cycle 1, each patient must be assessed by the Investigator as to whether or not the patient experienced a DLT. This information must be recorded on the appropriate eCRFs, and an electronic DLT notification (either DLT or not) will be sent to the Sponsor, before a subsequent cycle may begin.

Potential and IMP-related DLTs will be considered as adverse event of special interest (AESI). As such, the Investigators will be required to report them to the Sponsor within 24 hours of the Investigator becoming aware of each event. The Investigator will complete the specific DLT form in the eCRF.

The reported potential DLTs will be reviewed by the Study Committee in order to determine their relationship to the IMP.

9.1.2 Adverse events

Adverse events will be collected from the signing of the study main informed consent up to 30 days after the last IMP administration. During the follow-up period, ongoing SAEs regardless of relationship to IMP and ongoing or new study treatment related AEs will be followed until resolution or stabilization. Adverse events encountered before the start of study treatment will be summarized separately.

Adverse events will be graded according to the NCI CTCAE v.4.03, and will be coded to a “Preferred Term” and associated primary “System Organ Class” using MedDRA (Medical Dictionary for Regulatory Activities).

The study-specific and general safety criteria are developed in [Section 10](#).

9.1.3 Laboratory safety variables

Please refer to “Study Procedures” [Section 12](#).

9.1.4 Clinical examinations

Please refer to “Study Procedures” [Section 12](#).

9.1.5 Immunogenicity

It is of utmost importance to collect all blood samples at the specified times and according to the specifications for collection, storage, and shipment as defined in a separate laboratory manual.

Samples missed or lost, for any reason should be recorded. Actual dates and times of blood collection should be recorded in the eCRF. The dates and times of drug administration should also be precisely recorded.

The cemiplimab and isatuximab ADA sampling times for blood collection can be found in the PK Flow Chart ([Section 1.2](#) and [Section 1.3](#)).

- For cemiplimab during treatment phase, samples for immunogenicity assessment are to be collected every third Cycle from C5 (ie, on D1 of C5, C8, C11, C14, etc) till the last study treatment. In response to AEs of special interest, such as anaphylaxis or hypersensitivity, ADA samples closer to the event may be collected, based on the judgment of the Investigator and/or medical monitor. If isatuximab is stopped and cemiplimab treatment continues, cemiplimab ADA samples should be collected as planned per PK/PD flow-chart.
- For isatuximab, samples for immunogenicity assessment are to be collected during the course of the study. However, collection can be stopped earlier based on the updated knowledge of isatuximab immunogenicity (note that collection was indeed interrupted at cut-off date of primary efficacy analysis 6 months after LPI). At FU 90 (± 7) days after last IMP administration if ADA is positive or inconclusive no further ADA will be sampled. The ADA results will be communicated to investigational sites on an ongoing basis.

Bioanalytical methods used for immunogenicity assessment are summarized in [Table 7](#).

Table 7 - Bioanalytical methods for immune response assessment

Analyte	ANTI ISATUXIMAB ANTIBODY	ANTI CEMIPLIMAB ANTIBODY
Matrix	Plasma	Serum
Analytical technique	PandA method	Non-quantitative bridging immunoassay
Lower Limit of Quantification	Not applicable	Not applicable
Site of bioanalysis	Covance Harrogate (UK)	Regeneron Pharmaceuticals, Inc. (Tarrytown, NY)

9.2 EFFICACY

9.2.1 Primary endpoint (Phase 2 only)

The second co-primary endpoint of the study is to determine the efficacy of the combination as assessed by ORR. ORR is defined as the proportion of patients with CR (including sCR), VGPR and PR as assessed by investigators using the IMWG response criteria (44).

The following disease assessment procedures will be performed at screening (for eligibility) and again at Cycle 1 Day 1 prior to study treatment administration (baseline for response assessment) and then Day 1 of every cycle during treatment up to progression:

- M-protein quantification (serum and urine) (local laboratory).
- FLC quantification (local laboratory).
- Quantitative immunoglobulins (local laboratory).

- In addition, other examinations for disease assessment will be done as clinically indicated (eg, to confirm a response, suspected PD) as below (local laboratory):
 - Bone marrow aspiration,
 - Bone disease assessment,
 - Extramedullary disease (plasmacytoma) assessment (including bone plasmacytoma).

Response/progression will be determined according to IMWG criteria (44) ([Appendix D](#)). Response/progression based on M-protein and FLC will be confirmed based on 2 consecutive assessments.

Progressive disease is defined for patients with measurable disease with one of the following:

- Increase of $\geq 25\%$ in serum M-protein from nadir (the absolute increase must be ≥ 0.5 g/dL) in 2 consecutive assessments; serum M-protein increases ≥ 1 g/dL in 2 consecutive assessments are sufficient to define relapse if starting M-protein t is ≥ 5 g/dL and/or,
- Increase of $\geq 25\%$ in urine M-protein from nadir (the absolute increase must be ≥ 200 mg/24 h) in 2 consecutive assessments and/or,
- Only in subjects without measurable serum and urine M-protein levels: increase of $\geq 25\%$ in the difference between involved and uninvolved FLC levels and absolute increase must be > 10 mg/dL and/or,
- Definite development of new bone lesions or soft tissue extramedullary disease, or increase $\geq 50\%$ from nadir in the sum of perpendicular diameters of existing soft tissue extramedullary disease lesions if > 1 lesion, or $\geq 50\%$ increase in the longest diameter of a previous soft tissue extramedullary disease lesion > 1 cm in short axis.

Clinical deterioration will not be considered progression in the primary analysis of ORR.

Measurable disease is defined by at least one of the following measurement:

- Serum M-protein ≥ 1 g/dL or ≥ 0.5 g/dL for patients with IgA MM.
- Urine M-protein ≥ 200 mg/24h.
- In the absence of measurable M-protein, serum immunoglobulin FLC level ≥ 10 mg/dL provided abnormal serum immunoglobulin kappa lambda FLC ratio (< 0.26 or > 1.65).

9.2.2 Secondary endpoints (Phase 2 only)

- CBR: defined as the proportion of patients with CR (including sCR), VGPR, PR and minimal response (MR) as assessed by investigators using the IMWG response criteria.
- DOR: defined as the time from the date of the first response (\geq PR) that is subsequently confirmed to the date of first confirmed disease progression or death, whichever happens first PD will be determined according to IMWG criteria (See [Appendix D](#)). In the absence of the confirmation of subsequent disease progression or death before the analysis cut-off date or the date of initiation of a further anticancer treatment, the DOR will be censored at the date of the last valid disease assessment not showing disease progression performed

prior to initiation of a further anticancer treatment and the analysis cut-off date, whichever is earlier. DOR will not be calculated for patients that do not achieve a PR or better.

- TTR: defined as time from first study treatment administration (C1D1) to first response (PR or better) that is subsequently confirmed.
- PFS: defined as time from the first study treatment administration to the date of first documentation of progressive disease (PD) that is subsequently confirmed or the date of death from any cause. Same censoring rules as DOR will be used.
- OS: defined as the time from the first study treatment administration to death from any cause. Patients without death prior to the analysis cutoff date will be censored at the last date the patient was known to be alive or the cutoff date whichever comes first.

